9.2 Safety and Tolerability Outcome Measures

Safety outcomes:

1. AEs analyzed by frequency, NCI-CTC grade, and causality
2. Serious Adverse Events (SAEs) and events of special interest (injection site reactions, infections, new malignancy, tumor lysis syndrome)
3. Withdrawal rates, days and reasons for withdrawal
4. Dose modifications and treatment delays
5. Serum chemistry and hematology laboratory values; change from baseline and worst NCI-CTC grade

10 STATISTICAL METHODS

10.1 Descriptive Statistics

All measured variables and derived parameters will be listed individually and, if appropriate, tabulated by descriptive statistics.

For categorical variables, summary tables will be provided giving sample size, absolute and relative frequency and 95% CI (Confidence Interval).

For continuous variables, summary tables will be provided giving sample size, arithmetic mean, standard deviation, coefficient of variation (CV%), median, minimum and maximum and 95% CI (Confidence Interval) for means of variables.

The data will be analyzed using SAS/R.

10.2 Efficacy Endpoints

Efficacy will be evaluated by the investigator according to the 2006 IWG response criteria in MDS and for AML according to AML in Adults: 2017 ELN Recommendations from an International Expert Panel Revised (Döhner et al., 2017).

The analyses for efficacy will be performed for the following endpoints.

Overall Response Rate

The proportion of subjects with overall response ($OR = CR + mCR + PR + HI$) will be calculated. The 95% confidence interval for OR rate based on binomial distribution will be constructed.

Complete Remission Rate

The proportion of subjects with complete remission (CR) will be calculated. The 95% confidence interval for CR rate based on binomial distribution will be constructed.

Marrow Complete Remission Rate

The proportion of subjects with mCR with or without hematological improvement will be calculated. The 95% confidence interval for mCR rate based on binomial distribution will be constructed.

Partial remission (PR)

The proportion of subjects with PR with or without hematological improvement will be calculated. The 95% confidence interval for PR rate based on binomial distribution will be constructed.

Hematologic Improvement

The proportion of subjects with HI (erythroid/platelet/neutrophil responses) will be calculated. The 95% confidence interval for the rate of HI based on binomial distribution will be constructed.

Time to AML Transformation

Time to AML transformation will be defined as the number of days from the date of the first dose of study drug to the date of documented AML transformation. AML transformation will be defined as the presence of blast count $\geq 20\%$ in either the peripheral blood or bone marrow. Time to AML transformation will be summarized as median (range). Subjects who do not show transformation to AML will not be included in the analysis.

Duration of Response

Duration of response (DOR) will be defined as the number of days from the date of first response (CR, mCR, PR or HI) to the earliest documentation of progressive disease (PD). Duration of response will be analyzed by Kaplan-Meier methodology. Median DOR will be calculated and 95% confidence interval for median DOR will be presented.

If the response is still ongoing at the time of analysis, the subject's data will be censored at the date of the subject's last available disease assessment. For subjects who never experience a response, the subject's data will not be included in the analysis.

Overall Survival

Overall survival (OS) will be defined as the number of days from the date of the first dose of study drug to the date of death. Overall survival will be analyzed by Kaplan-Meier methodology. Median OS will be calculated and 95% confidence interval for median OS will be presented. Data from subjects that are alive at the time of analysis will be censored at the date of last study visit or the last known date the subject was alive, whichever is later.

Progression-Free Survival

Progression-free survival (PFS) will be defined as the number of days from the date of the first dose of study drug to the date of earliest disease progression or death due to disease progression or febrile neutropenia. Progression-free survival will be analyzed by Kaplan-Meier methodology. Median PFS will be calculated and 95% confidence interval for median PFS will be presented. All events of disease progression will be included regardless whether the event occurred while the subject was taking the study drug or had previously discontinued the study drug. Refer to Appendix 11 and 12 for the definition of disease progression. If the subject has not experienced disease progression or death, the subject's data will be censored at the date of last disease assessment. Data for subjects without any disease assessments performed after the first dose of study drug will be censored at the time of the first dose of study drug.

Event-Free Survival

Event-free survival (EFS) will be defined as the number of days from the date of the first dose of study drug to the date of earliest disease progression or death of any cause.

Event-free survival will be analyzed by Kaplan-Meier methodology. Median EFS will be calculated and 95% confidence interval for median EFS will be presented. All events of disease progression will be included regardless whether the event occurred while the subject was taking the study drug or had previously

discontinued the study drug. If the subject has not experienced disease progression or death, the subject's data will be censored at the date of last disease assessment. Data for subjects without any disease assessments performed after the first dose of study drug will be censored at the time of the first dose of study drug.

Safety assessments

AEs will be coded using the Medical Dictionary for Regulatory Activities (MedDRA). Incidence tables will be presented for all AEs by maximum grade graded according to the CTCAE, version 5). AEs, SAEs, deaths on study, AEs assessed as related to study drug and AEs resulting in dose reduction, interruption or discontinuation of study drug will be tabulated. Time-to-onset and duration of selected events will also be tabulated.

Laboratory assessments will be presented in shift tables of baseline grade vs. maximum grade on study, and summarized descriptively.

Study Drug Exposure

The number of days and/or cycles that subjects were exposed to study drug will be summarized.

General statistical considerations

Missing values will not be imputed. Outliers will be identified prior to the analyses of the efficacy endpoints and have to be checked by the study physician. According to the decision of the data management, the statistician and the study physician, outliers will be kept in the database or set to "missing".

Analysis datasets

Full analysis set (FAS)

All efficacy analyses will be conducted with the full analysis set (FAS). The full analysis set consists of all patients who were included in the study.

Per protocol analysis set (PPS)

The secondary dataset for analysis is derived from the per-protocol (PP) population. This dataset includes all trial subjects who were treated without major protocol violations.

Safety analysis set

The safety analysis set comprises all trial subjects who received any IMP or other trial treatment.

Sample size calculation

Based on AZARELA trial results, we assume that approximately 30% of responses due to AZA/DLI effects only might be observed. The objective is to demonstrate a 20% increase in response due to the addition of VENETOCLAX (i.e. from 30% to 50% after 6 cycles of AZA/DLI + VENETOCLAX).

For the phase I, a design "3+3" will be used, the number of subjects required for dose escalation will depend upon the occurrence of DLTs as the study progresses. Approximately 9 - 18 subjects may be enrolled to identify the MTD for venetoclax in combination with azacitidine.

For the phase II, a two-stage design will be used. With the assumption that the AZA/DLI gives 30 % of ORR, with the assumption that AZA/DLI + VENETOCLAX gives 50 % of ORR, and with an alpha risk of 0.05 and a beta risk of 80% with a drop-out of 10%, to confirm the safety and evaluate efficacy, for the phase II, 30 patients should be treated at the optimal dose (27 patients + drop-out of 10%).

Overall, a maximum of 48 patients will be treated: 9 - 18 in phase I and 30 in phase II.

Statistical analysis plan

Analysis will be based on an intent-to-treat basis, whether or not the patient receives the protocol treatment.

It will be performed once the sample size has been reached in each group, separately.

It will be based on the computation of response rate, with 95% confidence interval.

Randomization / Stratification

Not applicable for this trial.

Methods of Statistical analysis

A summary of the planned statistical analyses are described. Structured analyses will be specified in a separate statistical analysis plan (SAP) prior to the end of the data management process and before receiving final study data. If analyses should be conducted deviating from the following descriptions, these deviations also will be specified in the SAP prior to receiving final study data.

Descriptive Statistics

For continuous variables mean, standard deviation (SD), median, interquartile range, minimum and maximum will be presented.

For categorical variables absolute and relative frequencies will be presented.

Interim analysis

An interim analysis is planned during the phase II to evaluate the effectiveness of treatment.

If 3 responses or less are observed in the first 14 evaluable patients, there will be no further inclusions (the inclusions would be terminated early), but all patients on treatment and that continue to derive clinical benefit according to the opinion of the investigator while tolerating study-treatment may continue to receive treatment according to the protocol.

If 4 or more responses are observed, 16 additional patients will be included in the study.

Final analysis

The final report of the study and the compilation of the statistical report will be performed within 12 months after completion and correction of all case report forms (database lock).

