2 SUMMARY OF RATIONALE

a) MDS and AML in relapse after allo hematopoietic stem cell transplantation and their current treatment
Among patients with acute myeloid leukemia (AML), allogeneic hematopoietic stem cell transplantation (allo-HSCT) used as post-remission therapy for those with high-risk molecular profiles or as salvage therapy for those with resistant disease offers the highest potential for long-term survival[1]. In addition, allo-HSCT is the only curative option for patients with myelodysplastic syndromes (MDS) and chronic myelomonocytic leukemia (CMML)[2]. Still, relapse after allo-HSCT remains the major cause of treatment failure and is associated with a dismal prognosis[3]. Treatment options for those patients are mainly restricted to chemotherapy, donor lymphocyte infusions (DLI) or second allo-HSCT [4]. Treatment approach should ideally offer efficient antileukemic activity, acceptable toxicity and mechanisms to direct the donor immune system towards an enhanced graft-versus-leukemia effect without provoking graft-versus-host disease (GvHD). To fulfil all criteria, combination of azacitidine (AZA) to donor lymphocyte infusion (DLI) could be used in patients with relapse inferior to 2 years after allo-HSCT. AZA is approved for the treatment of patients with high-risk MDS and AML [5, 6]. Beyond its direct cytotoxic effects and ability to induce remissions even in patients refractory to chemotherapy, AZA is considered to increase the immunogenicity of AML blasts by re-expression of important antigens[7-9]. Furthermore, animal models suggest an immunomodulatory role of AZA that might attenuate GvHD after DLI [10, 11]. Combination was evaluated in AZARELA trial [12]. Treatment schedule contained up to eight AZA cycles (100 mg/m²/day, days 1–5, every 28 days) followed by DLI (from 1–5 x 10⁶ to 1–5 x 10⁸ CD3 cells/kg) after every second AZA cycle. A median of three courses AZA (range 1–8) were administered and 22 patients (73%) received DLI. Overall response rate was 30%, including seven complete remissions (CR, 23%) and two partial remissions (7%)[12, 13]. Incidence of acute and chronic

graft-versus-host disease was 37% and 17%, respectively. Azacitidine and DLI as salvage therapy is safe, induces long-term remission and is today a standard of care for patients in relapse after allo-HSCT [14].

b) VENETOCLAX

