3 HYPOTHESIS

Based on AZARELA trial results, we assume that approximately 30% of responses due to AZA/DLI effects only might be observed. The objective is to demonstrate a 20% increase in response due to the addition of VENETOCLAX (i.e. from 30% to 50% after 6 cycles of AZA/DLI + VENETOCLAX). For the phase I, a design "3+3" will be used including between 9 to 18 patients. For the phase II, a two-stage design will be used. Under $H_0=30\%$ and $p_1=50\%$, the study with $\alpha=0.05$ and $\beta=0.2$, if 3 responses or less are observed in the first 14 evaluable patients, there will be no further inclusions (the inclusions would be terminated early), but all patients on treatment and that continue to derive clinical benefit according to the opinion of the investigator while tolerating study-treatment may continue to receive treatment according to the protocol.

If 4 or more responses are observed, 16 additional patients will be included in the study. If 13 responses or more are observed in evaluable patients, further investigation is warranted to compare AZA/DLI and combination of AZA/DLI and VENETOCLAX. We consider that a maximum of 10% of the population may not be evaluable for response and that a total of 48 patients will be needed to address the question.

All patients on treatment and that continue to derive clinical benefit according to the opinion of the investigator while tolerating study-treatment may continue to receive treatment at the cohort-assigned dose level.

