5 STUDY ENDPOINTS

5.1 Primary endpoint

Phase I: To determine toxicity profile and safety of the combination

Phase II: Overall hematological response rate of venetoclax in combination with AZA/DLI

Response assessment will be performed according to modified IWG 2006 criteria for MDS and according European LeukemiaNet criteria for AML.

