6 INVESTIGATIONAL PLAN

6.1 Overall design

This is an open label multicenter phase I/II study. Patients will be treated with venetoclax during 14 days in combination with AZA at 75 mg/m²/day for 5 days for each cycle or 50 mg/m²/day for 5 days each cycle if relapse occurred less than 4 months after allo SCT.

Patients who meet eligibility criteria will be administered VENETOCLAX orally at starting dose in phase I part and at MTD in phase II part on days 1-14 in combination with AZA at 75 mg/m²/day for 5 days on days 1-5 for each cycle or 50 mg/m²/day for 5 days each cycle if relapse occurred less than 4 months after allo SCT.

Following cycles must be administered on day 28 or delayed until day 42 in cases of hematological toxicity. Each cycle will last 28 days starting on day 1 of each cycle when ANC > 1 G/L and platelet > 50 G/L without transfusion or when recovery of baseline level.

In the phase I part, VENETOCLAX will be given once daily orally on days 1-14 for all cycles at escalating doses starting at Dose Level 1 (defined below) in combination with AZA +/- DLI. Patients will receive at least 8 cycles of VENETOCLAX/AZA/DLI unless progression occurs. Response will be assessed after 4, 6 and 8 cycles. Patients achieving a response (see appendix 11 and 12) will be able to continue on protocol with VENETOCLAX + AZA until 12 cycles maximum then with AZA alone. In the absence of response, patients will stop treatment.

Dose Levels for Treatment in Phase I

Dose Level	VENETOCLAX (mg)	Azacitidine (mg/m ²)
-1	50 mg*	75 (50 if relapse < 4 months)
1 (Starting dose)	100 mg*	75 (50 if relapse < 4 months)
2	200 mg*	75 (50 if relapse < 4 months)
3	400 mg*	75 (50 if relapse < 4 months)

*VENETOCLAX will be given once daily orally during 14 days.

In the phase II part, VENETOCLAX will be given once daily orally on days 1-14 for all cycles at MTD defined in the phase I part of the study in combination with AZA/DLI. Patients will receive at least 8 cycles of VENETOCLAX/AZA/DLI unless progression occurs. Response will be assessed after 4, 6 and 8 cycles. Patients achieving a response (defined below) will be able to continue on protocol with VENETOCLAX + AZA until 12 cycles maximum then AZA alone. In the absence of response, patients will stop treatment.

Ramp-up** will be performed at the beginning of cycle 1:

Dose Level	VENETOCLAX D1C1	VENETOCLAX D2C1	VENETOCLAX D3C1 and beyond
-1	10 mg*	20 mg*	50 mg*
1 (Starting dose)	20 mg*	50 mg*	100 mg*
2	50 mg*	100 mg*	200 mg*

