9 CRITERIA FOR MEASUREMENT OF STUDY ENDPOINTS

9.1 Efficacy Outcome Measures

Primary Endpoint:

For MDS patients:

Overall response rate (ORR), defined as the proportion of patients who achieve a CR or PR per proposal for modification of the International Working Group (IWG) criteria for MDS, 2006 (Appendix 11):

1. CR is defined as bone marrow blasts $\leq 5\%$, without persistent dysplasia will be noted with normal maturation of all cell lines peripheral blood: Hgb ≥ 11 g/dL platelets $\geq 100 \times 10^9/L$, ANC $\geq 1.0 \times 10^9/L$, blasts 0%.
2. PR is defined as all CR criteria if abnormal before treatment except for bone marrow blasts decreased by $\geq 50\%$ over pretreatment but still $> 5\%$ cellularity.

For AML patients:

CR Rate, defined as the proportion of patients who achieve a CR per the ELN2017 criteria: CR is defined as BM blasts $< 5\%$, absence of circulating blasts and blasts with Auer rods, absence of extramedullary disease, ANC $\geq 1.0 \times 10^9/L$ (1,000/ μ L); platelet count $\geq 100 \times 10^9/L$ (100,000/ μ L).

Secondary Endpoints:

For MDS patients:

1. Overall improvement rate (OIR), defined as the proportion of patients reaching a CR, Marrow CR, PR, or hematologic improvement (HI) per proposal for modification of the IWG criteria for MDS, 2006 (Appendix 11). Marrow CR is defined as bone marrow blasts $\leq 5\%$ and decreased by 50% over pretreatment. Peripheral blood: if HI responses, they will be noted in addition to marrow CR. HI is defined as:
 - a. Erythroid response (pretreatment, < 11 g/dL) is defined as Hgb increase by ≥ 1.5 g/dL. Relevant reduction of units of red blood cells (RBC) transfusions by an absolute number of at least 4 RBC transfusions/8 weeks, compared with the pretreatment transfusion number in the previous 8 weeks. Only RBC transfusions given for a Hgb of ≤ 9.0 g/dL will count in the RBC transfusion response evaluation.
 - b. Platelet response (pretreatment $< 100 \times 10^9/L$) is defined as absolute increase of $\geq 30 \times 10^9/L$ for patients starting with $> 20 \times 10^9/L$ platelets, and an increase from $< 20 \times 10^9/L$ to $> 20 \times 10^9/L$ and by at least 100%.
 - c. Neutrophil response (pretreatment, $< 1.0 \times 10^9/L$) is defined as at least 100% increase and an absolute increase $> 0.5 \times 10^9/L$

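### The phase II primary response is defined differently in sections 9.1 and 10.2, and neither definition matches the CR+PR basis of the 30% null

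*Protocol*

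**What the plan says.** Section 5.1 names the endpoint without its components: "Phase II: Overall hematological response rate of venetoclax in combination with AZA/DLI". It refers to IWG 2006 for MDS and European LeukemiaNet (ELN) criteria for AML.

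The definitions then diverge:

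- **Section 9.1, primary, MDS:** "Overall response rate (ORR), defined as the proportion of patients who achieve a CR or PR per proposal for modification" of the IWG criteria, i.e. CR+PR.
- **Section 9.1, primary, AML:** "CR Rate, defined as the proportion of patients who achieve a CR per the ELN2017 criteria", i.e. CR alone.
- **Section 9.1, secondary, MDS:** CR, marrow CR (mCR), PR or HI, called the overall improvement rate (OIR).
- **Section 9.1, secondary, AML:** CR+CRi, also called overall response rate.
- **Section 10.2, Overall Response Rate:** "The proportion of subjects with overall response ($OR = CR + mCR + PR + HI$) will be calculated", with no split by disease.

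Duration of response follows the same divide. Section 10.2 starts it at CR, mCR, PR or HI; section 9.1 starts it at PR/CR in MDS and CR/CRi in AML.

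The null comes from the reference trial of azacitidine plus DLI in section 2: "Overall response rate was 30%, including seven complete remissions (CR, 23%) and two partial remissions (7" (the quotation is cut at the 7% figure). Section 3 sets the target, "i.e. from 30% to 50% after 6 cycles of AZA/DLI + VENETOCLAX", and the rule: stop at 3 or fewer responses in 14, otherwise add 16 patients, with 13 or more responses counting as success.

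**The concern.** One response rate drives both phase II decisions, and the protocol defines it in ways that can classify the same patient differently. An MDS patient whose best result is marrow CR or HI is a non-responder under section 9.1 and a responder under section 10.2. An AML patient in PR is a non-responder under section 9.1, yet a similar patient in the reference trial counted towards the 30%.

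A single-arm comparison with a fixed historical rate is interpretable only if the observed rate and the null count the same things. Here a wider count raises the chance of passing without any drug effect, and a narrower count lowers power. The trial is open label and response is judged by the investigator, so leaving the choice of section open until data are known would be hard to defend.

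**Working it through.** **Inputs from the protocol**

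- p0 = 0.30, p1 = 0.50, alpha = 0.05, beta = 0.20 (section 3).
- Stage 1: continue with at least 4 of 14. Final: success with at least 13 of 14 + 16 = 30 (section 3).
- Null composition: 7 CR (23%) and 2 PR (7%) (section 2). Since 7/0.23 ≈ 30, this is 9/30 = 30%, and the CR-alone rate is 7/30 = 23.3%. The second azacitidine plus DLI series in section 2, 33% = 27% CR + 6% PR, is also CR+PR.

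**Inputs the protocol does not give (assumed)**

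- Share of patients on azacitidine/DLI alone with mCR or HI but no CR or PR: 5 to 20 points.
- MDS/AML split: one half each for illustration, with all-AML as the extreme.

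**Formula.** For a true response rate p,

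P(pass) = Σ over x = 4 to 14 of C(14,x) p^x (1−p)^(14−x) × P(Y ≥ 13−x), with Y ~ Binomial(16, p).

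**Step 1: the plan's own figures.** At p = 0.50, P(pass) = 0.814, which agrees with the planned 80% power. At p = 0.30, P(pass) = 0.083, not 0.05. That excess is present with any definition whose true null rate is 30%, so 0.083 is the baseline below.

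**Step 2: wide definition (section 10.2), no venetoclax effect.** CR+PR stays at 30% and mCR/HI adds d points.

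| d | Added trial-wide: p, P(pass) | Added in MDS only, MDS = half: p = 0.30 + d/2, P(pass) |
|---|---|---|
| 0 | 0.300, 0.083 | 0.300, 0.083 |
| 5 | 0.350, 0.216 | 0.325, 0.140 |
| 10 | 0.400, 0.416 | 0.350, 0.216 |
| 15 | 0.450, 0.634 | 0.375, 0.310 |
| 20 | 0.500, 0.814 | 0.400, 0.416 |

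**Step 3: narrow definition for AML (section 9.1).** Assume that the reference trial's CR and PR rates apply to both diseases. With AML share m, the matching null is 0.30(1−m) + 0.2333m. Power is taken at that null plus 20 points, with the 13/30 bound unchanged.

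| AML share m | Matching null | P(pass) at null | Power at null + 20 points |
|---|---|---|---|
| 0 | 0.300 | 0.083 | 0.814 |
| 0.5 | 0.267 | 0.035 | 0.701 |
| 1.0 | 0.233 | 0.012 | 0.563 |

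**The case against.** Several points can fairly be made for the protocol.

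- **Section 10.2 does not call its composite primary.** True. But it is the only overall-response analysis there, it shares its name with the rate used in the sample-size paragraph, and no analysis in section 10.2 combines CR and PR alone. A later SAP could settle the matter only by contradicting one section.
- **The formula need not inflate the AML count.** A reader might infer that section 10.2 adds mCR and HI for every patient. The documents do not establish this. The section opens by assigning ELN 2017 to AML, and the ELN categories in Appendix 12 contain neither. On that reading the formula reduces to CR+PR in AML and only MDS patients inflate the rate. The reading is not certain, because section 6.1 lists mCR and HI as grounds for continuing in a sentence that also names AML criteria. Both cases are therefore shown.
- **CR alone for AML is conservative.** This stands for the false-positive risk (0.012 in an all-AML trial), at the price of power. A larger loss, to 0.37, follows only if every patient has AML and the 20-point CR+PR gain splits 7:2 between CR and PR. The documents support neither premise.
- **The time points do not conflict.** Section 6.1 says "Response will be assessed after 4, 6 and 8 cycles", which is a visit schedule, and the cycle 6 reading named in the hypothesis is one of those visits. At most, section 9.1 fails to restate it.

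**Conclusion.** The definitional conflict is in the current text and needs correction before either phase II decision is made. Section 9.1 and section 10.2 give different primary responses, and neither matches the CR+PR basis of the 30%.

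The direction of each error is clear; the size is conditional. The wide definition raises the no-effect pass probability from 0.083 to somewhere in 0.14–0.42 (MDS only, half the trial) or 0.22–0.81 (trial-wide), for an assumed 5 to 20 points of mCR/HI. The protocol gives neither that rate nor the disease split, so a reader should not take 0.81, or any other single figure, as the trial's false-positive rate. CR alone for AML lowers power for a 20-point gain from 0.81 to about 0.70 with half AML and 0.56 with all AML, if the reference rates hold in both diseases.

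The gap between 0.083 and the stated alpha of 0.05 is a separate design fault. It should not be attributed to the definitions, and aligning them does not remove it.

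**What to change.** 1. State one primary response in sections 5.1, 9.1 and 10.2 on the same basis as the null: CR+PR, by IWG 2006 in MDS and ELN 2017 in AML. If the sponsor prefers CR alone in AML, derive the null from CR for that group and recompute the 14- and 30-patient bounds.
2. State in section 9.1 that the decision uses response by the cycle 6 assessment, as the hypothesis has it. The reference trial allowed up to eight azacitidine cycles and section 2 gives no response window, so this follows the hypothesis and is not shown to match the source of the 30% on timing.
3. Keep CR+mCR+PR+HI as the secondary OIR for MDS. Keep CR/CRi as an AML secondary under a name other than overall response rate.
4. Align the starting event for duration of response in section 10.2 with section 9.1.

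The cost of the CR+PR option is wording, and a headline rate that may be lower than with mCR and HI included. Keeping CR alone in AML also means recalculating the design, possibly with a different sample size.
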